**Objectives**

**Overall objectives**

SPECIFIC AIMS Primary Aim: To determine if the efficacy of prophylaxis with a 24 hour course of methenamine hippurate (two doses) is non-inferior to the efficacy of a 24-hour course of fluoroquinolones in prevention of post-operative urinary tract infections after short-term indwelling catheterization following surgery for pelvic floor disorders. Secondary aim: - To determine if prophylaxis with methenamine hippurate is more cost-effective than prophylaxis with fluoroquinolones

in patients undergoing short-term indwelling catheterization. - To determine the antibiotic resistance profile of post-operative urinary tract infections that develop after short-term indwelling catheterization after surgery for pelvic floor disorders, with methenamine as compared to fluoroquinolones. - To determine the prevalence of side effects that may accompany use of methenamine hippurate prophylaxis. - To describe factors that influence patient medication compliance with short-term methenamine hippurate and ciprofloxacin prophylaxis.

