#### **Primary outcome variable(s)**

PRIMARY OUTCOME: Treatment of clinically suspected UTI within three weeks of surgery. This is defined as any symptomatic UTI requiring treatment with antibiotics as determined by the development of 2 or more of the following symptoms, in the absence of vaginal symptoms: urinary frequency; urinary urgency; dysuria; fever over 38°C/100.4°F; suprapubic, flank, or back pain; and/or chills. Patients will be encouraged to undergo urine culture prior to empiric treatment, but a positive urine culture will not be required as part of the primary outcome. We feel that this more accurately reflects the diagnosis and treatment of UTI in the clinical setting as: 1) it may not always be possible to delay treatment until patients are able to undergo urine culture; 2) accuracy of self-reported symptoms for the diagnosis of UTI is high; 3) the probability of UTI in patients with combinations of symptoms is very high.

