#### **Secondary outcome variable(s)**

SECONDARY OUTCOME: - cost-effectiveness of prophylaxis with methenamine hippurate for prevention of post-operative UTI compared to prophylaxis with fluoroquinolones - rate of culture-positive symptomatic UTI - prevalence of antibiotic resistance in positive post-operative cultures - prevalence of side effects following a 24-hour course of methenamine hippurate - factors that may influence patient compliance with short-course of chemoprophylaxis. Cost-effectiveness data: We plan to perform a cost-effectiveness analysis from a societal perspective, which will be expressed as incremental cost per UTI prevented. Routine costs of prevention of UTI with methenamine hippurate prophylaxis will be compared with costs of prevention of UTI with fluoroquinolone prophylaxis. We plan to capture incremental direct health care costs, which will be estimated using the resource costing method. Direct medical service standard of care use (such as number and types of physician visits, hospital admissions lengths, emergency transport and emergency room visits), and direct medical costs (such as antibiotic treatment of UTI, prophylaxis with methenamine or ciprofloxacin, urine laboratory tests, or treatment of complications like pyelonephritis) will be monetized by multiplying the number of units of each resource used per treatment arm by the average unit cost of these items in dollars. Detailed individual cost data will not be collected. This method allows a consistent capture of resource use when costs are incurred across multiple health systems or payers. Cost for each direct medical service use, direct non-medical items, and indirect items will be assigned based on national Medicare reimbursement rates or other standardized unit costs. Among patients who undergo urine culture as part of standard of care for UTI, the rate of positive cultures will be identified. As per standard of care, antibiotic resistance will be collected by sensitivity testing on all positive urine cultures identified from samples collected for evaluation of symptomatic UTI in post-operative patients. Bacterial species and sensitivities will be identified and recorded. To determine medication compliance rates, any unused medication will be returned to the office at their post-operative follow-up visit. As per routine care, investigators will also ask patients during the weekly routine post-operative call and routine post-operative visits about their compliance with the second dose of medication. Adverse effects from the administration of methenamine and fluoroquinolones will be collected. Patients will be asked to document any side effects, including nausea, vomiting, pruritis, and rash, that may occur within 24 hours of the administration of the last dose of methenamine or antibiotic.

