### **Accrual**

This trial will be an non-inferiority trial, intended to determine if a short course of methenamine hippurate is no worse than a short course of fluoroquinolones (ciprofloxacin at Pennsylvania Hospital, levofloxacin at HUP, based on current practice and fluoroquinolone availability at each site) in prevention of post-operative UTI in short-term indwelling catheterization. Our primary outcome is the treatment of UTI by symptoms, a clinically relevant outcome. In the only study to look at this primary outcome after treatment with prophylactic antibiotics during short-term catheterization in urogynecologic surgery, the percentage of patients requiring treatment for UTIs after prophylactic antibiotics was 22%. If we assume a non-inferiority margin of 15%, a clinically relevant margin and commonly used in non-inferiority/equivalence trials for studies examining antibiotic use for urinary tract infections, as well as 80% power and a one-sided alpha of 0.025, 120 participants in each arm (total of 240 patients) will be required. Of all patients that undergo pelvic reconstructive surgery at our institution, approximately 75% are discharged home with an indwelling catheter. With a potential 15% drop-out rate, we therefore anticipate that we will need to recruit about 370 eligible patients in our clinics. As listed before, review of the surgeons logs over the last 12 months shows that this study is feasible due to the large volume of pelvic reconstructive surgery procedures in Urogynecology and Urology. Last year, the combined surgical volume of these cases at our three clinics was 532 subjects; thus, we anticipate we will be able to easily recruit the proposed sample size in one year. We plan to

recruit women from 4 sites in 3 departments in the University of Pennsylvania Health System: 1) Urogynecology at Hospital of University of Pennsylvania (HUP), 2) Urogynecology at Pennsylvania Hospital (PAH) and 3) Urology at Pennsylvania Hospital (PAH). Physician investigators are present at all three sites, and will have opportunity to screen patients planning for surgery for pelvic organ prolapse, urinary incontinence, or both, for participation.

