
medication they are taking. The methenamine, ciprofloxacin, and levofloxacin used in this study are all similar in shape, although not in color. Following catheter removal one to two hours after the first dose of medication, patients will be given a white vial or bag with the second dose of medication (if given methenamine or ciprofloxacin) and will be instructed to take second dose of the study medication at home about 12 hour later. As part of standard of care, nurses perform void trials per practice guidelines by backfilling the bladder with 300 cc normal saline, removing the catheter, and prompting the patient to void immediately. If a patient fails her trial of void, majority of the patients at our site are taught intermittent self-catheterization. If an indwelling catheter is replaced, the allocated treatment (drug or placebo) will be re-administered at repeat trial of void/repeat catheter withdrawal. No further drug will be given if the patient performs intermittent self-catheterization after the failed trial of void. FOLLOW UP VISITS: Three weekly follow-up calls and one postoperative visit are planned. It is standard of care of our clinical practices in the office for a clinical urogynecology nurses to routinely contact patients post-surgery to ask about any symptoms or complications from the procedures they underwent. In this study, per routine office practice, urogynecology nurses will call study participants once a week for the first three weeks following surgery. As per routine, using a structured form, patients will be asked about symptoms of UTI, any treatment for UTI, any urine laboratory testing, visits, and treatment for suspected UTI from other providers other than the urogynecology clinic (e.g. ER, primary care doctor), treatment of complications secondary to UTI (such as pyelonephritis and sepsis), and any additional use of antibiotic for infections other than UTI. Questions related solely to the study medication will include compliance with medications given, and side effects within 24 hours of taking medication. At any time during the study, as per standard of care of all urogynecology patients, patients who feel that they may have UTIs will be encouraged to call the urogynecology clinical nurses or the on-call physician with their symptoms. These encounters, any testing, and any empiric treatment are documented in the electronic medical system. If the diagnosis of UTI is unclear at any time, per standard of care, the patient will be asked to come into the office for physical examination and further diagnostic testing. If patients are suspected of having UTI, treatment for UTI will be initiated. As per routine office care for treatment of UTI, if possible, all patients will be asked to give a specimen for urinalysis and urine culture prior to beginning empiric treatment. Four to eight weeks following surgery, as per standard of care, patients will return to the office for a routine post-operative assessment with the investigating physicians. The patients will undergo routine post-operative physical examination and answer the above questions. Any methenamine or ciprofloxacin that has not been taken as instructed will be returned at this time. At their post-operative visit, the patient will be asked if they were aware of which medication they were taking to assess blinding.

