**Analysis Plan**

Categorical variables will be analyzed using chi-squared or Fishers exact test and parametric or non-parametric t-tests for continuous variables. Bivariable analysis will be used to determine variables (risk factors) that are independently associated with post-operative UTI. Duration of catheterization between groups will be compared using the Mann-Whitney test to compare difference in medians. The primary outcome will be the rate of clinically suspected UTI requiring treatment within the first three weeks following surgery. Comparison with fluoroquinolones will be performed using relative risk ratio. Analysis will be performed by intention to treat. If imbalances in baseline demographics are identified, multivariate analyses for post-operative UTI will be performed to control the inequality. Cost-effectiveness analysis will be performed by monetizing the collected resource utilization data in each treatment arm, including use of intervention resources, UTI treatment resources, as well as primary and secondary care resources. Incremental cost-effectiveness ratios will be calculated to compare difference in costs between prophylaxis with methenamine and prophylaxis with fluoroquinolones to the difference in effect on the incidence of post-operative UTI. Prevalence of adverse effects will be measured as

percentages. Rate of urine cultures performed by patients treated for symptomatic UTI, as well as the rate of culture-positive UTI will be noted; comparison with fluoroquinolones will be performed using relative risk ratio, with analysis by intention to treat. Positive cultures will be analyzed for percentage of uropathogen type, type of uropathogen showing resistance, and overall percentage of cultures showing resistance.

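### The between-arm resistance aim is measured only as a share of positive cultures, a denominator that arises after randomisation and can move with the drug given

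*Combined protocol and SAP*

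**What the plan says.** Under Overall objectives, a secondary aim is to determine the resistance profile of post-operative UTIs "with methenamine as compared to fluoroquinolones", so the aim is a comparison between arms.

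Secondary outcome variable(s) defines the outcome as "prevalence of antibiotic resistance in positive post-operative cultures". The Analysis Plan then states: "Positive cultures will be analyzed for percentage of uropathogen type, type of uropathogen showing resistance, and overall percentage of cultures showing resistance". It names no effect measure, test or all-randomised denominator for resistance. No section plans resistant infections per randomised woman.

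A positive culture requires a suspected UTI, a specimen and growth. Primary outcome variable(s) says: "Patients will be encouraged to undergo urine culture prior to empiric treatment, but a positive urine culture will not be required" for the outcome. Procedures says that "if possible, all patients will be asked to give a specimen for urinalysis and urine culture prior to beginning empiric treatment".

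For culture positivity two descriptions stand side by side. Secondary outcome variable(s) says: "Among patients who undergo urine culture as part of standard of care for UTI, the rate of positive cultures will be identified". The same section also lists the rate of culture-positive symptomatic UTI as an outcome. For that rate, and for the rate of culturing among treated women, the Analysis Plan says that "comparison with fluoroquinolones will be performed using relative risk ratio, with analysis by intention to treat". It does not spell out the denominator.

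**The concern.** Randomisation makes the two groups of randomised women comparable. It does not make the two groups of women with a positive culture comparable, because the study drug helps decide who enters them. A fluoroquinolone can be expected to act mainly on fluoroquinolone-susceptible organisms. Each susceptible infection it prevents leaves the denominator, while the resistant infections stay, so the resistant share rises without one additional resistant infection.

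The planned percentage therefore cannot tell apart two different findings: that fluoroquinolone prophylaxis led to more resistant infections, or that it prevented more susceptible ones. The first would support the rationale for a non-antibiotic agent. The second is a benefit of the antibiotic that would look like a harm. Limiting resistance is a central part of the case for methenamine in the Background and Potential Study Benefits sections, so readers are likely to look at this comparison.

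**Working it through.** **Inputs from the documents**
- UTI treatment rate after antibiotic prophylaxis 22%, non-inferiority margin 15 points, 80% power, one-sided alpha 0.025, 120 per arm (Accrual).
- Ciprofloxacin resistance 29% and ampicillin resistance 59% in a survey of nosocomial UTI (Background).

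**Sample size first.** With 22% in both arms, n = (1.960 + 0.842)² × 2 × 0.22 × 0.78 / 0.15² = 7.85 × 0.3432 / 0.0225 ≈ 119.7, so 120 per arm. The stated figure reproduces, which implies that equal UTI rates were the planning assumption. The documents give no figure for the resistance comparison. Study duration still mentions 72 per arm; that would change the counts below but none of the percentages.

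**Assumptions for the illustration**
- 29% of methenamine-arm infections are fluoroquinolone-resistant.
- The number of resistant infections is the same in both arms, so any extra fluoroquinolone effect falls on susceptible infections only.
- Every UTI is cultured and positive.

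**Formulas.** Let m and f be the UTI risks in the methenamine and fluoroquinolone arms.
- Resistant risk per randomised woman, both arms: r = 0.29 × m.
- Resistant share of positives: 29% with methenamine, r / f with fluoroquinolone.
- Share of methenamine-arm susceptible infections that the fluoroquinolone would have to prevent in addition: (m − f) / (0.71 × m).

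| UTI, methenamine vs fluoroquinolone | Extra susceptible prevented | Resistant infections in each arm of 120 | Risk per randomised woman, both arms | Resistant share of positives | Ratio |
|---|---|---|---|---|---|
| 22% vs 22% | 0% | 7.7 | 6.4% | 29.0% vs 29.0% | 1.00 |
| 29.5% vs 22% | 36% | 10.3 | 8.6% | 29.0% vs 38.9% | 1.34 |
| 37% vs 22% (at the margin) | 57% | 12.9 | 10.7% | 29.0% vs 48.8% | 1.68 |
| 22% vs 15% | 45% | 7.7 | 6.4% | 29.0% vs 42.5% | 1.47 |
| 22% vs 11% | 70% | 7.7 | 6.4% | 29.0% vs 58.0% | 2.00 |

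In every row the risk ratio per randomised woman is 1.00. Culturing 50% or 70% of UTIs, equally in both arms, leaves the shares unchanged and shrinks the counts.

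**Resistance to any drug.** The Analysis Plan does not restrict resistance to fluoroquinolones. Suppose 59% of methenamine-arm isolates are resistant to some drug, all fluoroquinolone-resistant isolates lie within that 59%, and half of the fluoroquinolone-susceptible infections are prevented evenly. Per 100 methenamine-arm infections, the fluoroquinolone arm keeps 29 + 71/2 = 64.5, of which 29 + (59 − 29)/2 = 44 are resistant to some drug. The share is 44/64.5 = 68% against 59% (ratio 1.16). For fluoroquinolone resistance on the same assumption it is 29/64.5 = 45% against 29% (ratio 1.55).

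**Precision.** At 22% UTI there are at most 0.22 × 120 ≈ 26 positives per arm, or about 13 if half are cultured. The 95% half-width for a difference in resistant share near 29% is 1.96 × √(2 × 0.29 × 0.71 / 26) ≈ 25 points, and about 35 points with 13. Per randomised woman at 6.4% in both arms it is 1.96 × √(2 × 0.064 × 0.936 / 120) ≈ 6 points.

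**The case against.** **The resistance analysis is already descriptive.** The Abstract speaks of describing the resistance profile, and the Analysis Plan attaches no test to it. This stands in part: no formal inference on the percentage is planned. But the Objectives word the aim as a comparison, and the percentage is the only measure available for making it. The intention-to-treat clause does not help, since it belongs to the preceding sentence on culture rate and culture-positive UTI.

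**The artefact is conditional.** This stands. It requires fluoroquinolones to prevent more susceptible infections than methenamine does, and to spare resistant ones relative to susceptible ones. A reader might infer that the planned percentage is bound to favour methenamine; under the equal UTI rates behind the sample size, with equal resistant counts, the ratio is 1.00.

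**The largest figures concern one drug class.** This stands too. For the any-drug percentage that is planned, the direction holds but the gap is smaller.

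**Culture positivity is already handled.** Largely true. A reader of Secondary outcome variable(s) alone might infer that culture positivity is compared between arms as a percentage of cultures taken. The Analysis Plan does not support that: it compares the rate of culture-positive UTI by relative risk under intention to treat. The rate among cultured women can be read as a separate descriptive yield. What remains is an unstated denominator. Incomplete culturing is also not ignored, because the culture rate among treated women is already a planned comparison.

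**The data are too sparse to mislead.** Intervals of 25 to 35 points either way would not support a firm claim. That limits the harm, but the plan mentions no interval for resistance, and bare percentages of 29% and 49% can be over-read.

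**Conclusion.** The point holds for resistance. The aim is comparative, the only planned measure is conditional on a positive culture, and that condition is affected by treatment. With no difference in resistant infections per randomised woman, the illustrated resistant share is 1.34 to 1.68 times as high in the fluoroquinolone arm for UTI differences of half the margin and the full margin, and up to 2.00 times in the most extreme scenario examined. It is 1.00 when susceptible infections are prevented equally.

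These sizes rest on the assumed 29%, on equal resistant counts, and on complete or equal culturing. The documents give no expected resistance or culture rate for this trial, so they show what could happen rather than what is expected. For culture-positive UTI the documents need only a clarifying sentence.

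This is a worthwhile, inexpensive correction to a secondary outcome. The primary outcome, its analysis and the sample size are unaffected.

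**What to change.** 1. In the Analysis Plan, define the between-arm resistance comparison as the number of women with a resistant culture-positive UTI divided by all women randomised, by arm, as a risk difference with a 95% confidence interval. Do the same separately for fluoroquinolone-resistant culture-positive UTI.
2. Keep the percentage of positive cultures showing resistance, and the uropathogen breakdown, as description only, with numerators and denominators shown.
3. State that the intention-to-treat comparison of culture-positive UTI uses all randomised women, and that the rate among cultured women in Secondary outcome variable(s) is descriptive.
4. Show the already planned culture rate among treated women beside these results, by arm. A woman treated without a culture cannot count as a resistant case, so the new measure undercounts when culturing is incomplete, and the reader needs to see whether that differs by arm.

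**Cost.** This changes analysis-plan wording only. Species and sensitivities of positive cultures are already to be recorded. Events will be few (about 8 to 13 per arm in the scenarios above, fewer if not every UTI is cultured), so the intervals will be wide relative to the risks and should be reported as such.

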**The following documents are currently attached to this item:**

*There are no documents attached for this item.*

**Data confidentiality**

**x Paper-based records will be kept in a secure location and only be accessible to personnel involved in the study.**

**x Computer-based files will only be made available to personnel involved in the study through the use of access privileges and passwords.**

**Prior to access to any study-related information, personnel will be required to sign statements agreeing to protect the security and confidentiality of identifiable information.**

**x Wherever feasible, identifiers will be removed from study-related information.**

**A Certificate of Confidentiality will be obtained, because the research could place the subject at risk of criminal or civil liability or cause damage to the subject's financial standing, employability, or liability.**

**A waiver of documentation of consent is being requested, because the only link between the subject and the study would be the consent document and the primary risk is a breach of confidentiality. (This is not an option for FDA-regulated research.)**

**Precautions are in place to ensure the data is secure by using passwords and encryption, because the research involves web-based surveys.**

**Audio and/or video recordings will be transcribed and then destroyed to eliminate audible identification of subjects.**

**Subject Confidentiality**

Extensive efforts will be made to ensure and maintain participant confidentiality. Data from patients will be recorded on data collection forms, which will be associated with a Subject ID number only. The patient name, medical record numbers, or other identifiers will not be present on the data collection forms themselves. The 6-digit Participant ID number will be composed by the sequential ordering of participants. At each site, a log book will be kept in for data management purposes to match Subject ID number with patient medical record numbers if chart review is needed for missing data. This will also be maintained in a secure and locked filing system at all times. Any additional source documentation that may associate the patient and PHI to data (such as consent forms) will also be kept in a secure and locked filing system at all times. Additionally, any data collection forms will also be kept in a separate secure and locked filing system at all times. At the University of Pennsylvania, the participant will be logged in the Excel spread sheet using their assigned Subject ID number. The Excel spreadsheet form will be stored in a password-secured file and a physical backup copy of this file will be made at the end of every other week and the copy stored in a separate, secure area/filing system.

